## 2.6 Treatments (study drug, concomitant therapies, compliance)

The Safety Set will be used for all medication data summaries and listings unless otherwise specified.

### Study drug and study treatment

Study drug and study treatment both refer to LDK378 and will be used interchangeably.

### Date of first/last administration of study drug

The date of first administration of study drug is defined as the first date when a non-zero dose of study drug was administered and recorded on the Dosage Administration Record (DAR) eCRF. For the sake of simplicity, the date of first administration of study drug will also be referred to as start date of study drug.

The date of last administration of study drug is defined as the last date when a non-zero dose of study drug was administered and recorded on DAR eCRF. This date will also be referred to as last date of study drug.

### Study day

The study day for all assessments (e.g. tumor assessment, death, disease progression, tumor response, performance status, adverse event onset, laboratory abnormality occurrence, vital sign measurement, dose interruption) will be calculated using the start date of study drug as the origin. For assessments occurring after or on the start date of study drug, study day will be calculated as:

$$\text{Study Day} = \text{Event date} - \text{start date of study drug} + 1.$$

The first day of study drug is therefore study day 1.

For any assessment or events such as baseline disease characteristics or medical history (e.g., time since diagnosis of disease) occurring prior to the start of the study drug, study day will be negative and will be calculated as:

$$\text{Study Day} = \text{Event date} - \text{start date of study drug}$$

The study day will be displayed in the data listings.

### Dose exposure and intensity

Definitions of duration of exposure, cumulative dose, average daily dose, actual dose intensity (DD), relative dose intensity (RDI), as well as intermediate calculations, include:

- Duration of exposure (days): last date of study drug - first date of study drug + 1 (periods of interruption are not excluded)
- Cumulative dose (mg): total dose of study drug taken by a patient in the study
- Number of dosing days (days): duration of exposure - number of zero dose days
- Average daily dose (mg/day): cumulative dose (mg) / number of dosing days (days)
- DI (mg/day): cumulative dose (mg) / duration of exposure (days)
- RDI (%):  $100 \times [\text{DI (mg/day)} / \text{planned dose (750 mg)}]$

Note: given the planned LDK378 dose of 750mg/day, the planned dose intensity can be calculated as  $\text{PDI (mg/day)} = \text{cumulative planned dose (mg)} / \text{Duration of exposure (days)}$ , where cumulative planned dose (mg) = Protocol planned dose of 750 (mg) \* Duration of exposure. RDI (%) which is calculated as  $100 * \text{DI} / \text{PDI}$  can be simplified as shown above.

Duration of study exposure to study drug, cumulative dose, average daily dose, DI and RDI will be summarized. In addition, the duration of exposure to study drug will be categorized into time intervals; frequency counts and percentages of patients with exposure in each time interval will be presented. Frequency counts and percentages of patients who have dose changes, reductions or interruptions, and the corresponding reasons, will be summarized.

Listings of all doses of the study drug along with dose change/interruption reasons will be produced.

[Section 4.5](#) provides further details on the definition of dose changes and interruptions.

### Concomitant therapy

Concomitant therapies are defined as any medications (excluding study drug, prior antineoplastic treatments and blood transfusions), surgeries or procedures (including physical therapy) administered in the study and are recorded in the Prior and Concomitant Medications and the Surgical and Medical Procedures eCRF, respectively.

These therapies will be coded using the WHO Drug Reference Listing (WHO DRL) dictionary that employs the WHO Anatomical Therapeutic Chemical (WHO ATC) classification system. All summaries will be tabulated using frequency counts and percentages.

Concomitant therapies will be summarized by ATC class and preferred term. These summaries will include 1) medications starting on or after the start of study drug but starting

no later than 30 days after last dose of study drug and 2) medications starting prior to the start of study drug but continuing after the start of study drug.

All concomitant therapies will be listed. Any concomitant therapies starting and ending prior to the start of study drug or starting more than 30 days after the last date of study drug will be flagged in the listing.

### **Antineoplastic therapy after discontinuation of study drug**

The FAS will be used for all listings and summaries of antineoplastic therapies initiated after discontinuation of study drug. All summaries will be tabulated using frequency counts and percentages.

Antineoplastic medications initiated after discontinuation of study drug will be summarized and listed by Anatomical Therapeutic Chemical (ATC) class and preferred name.

Antineoplastic radiotherapy since discontinuation of study treatment will be summarized and listed by setting.

Antineoplastic surgery since discontinuation of study treatment will be summarized and listed by procedure.

## **2.7 Analysis of the primary variable**

The primary objective is to demonstrate the antitumor activity of LDK378, as measured by ORR by investigator assessment.

### **2.7.1 Variable**

The primary endpoint used to evaluate the anti-tumor activity of LDK378 is the overall response rate (ORR), defined as the proportion of patients with a best overall confirmed complete response (CR) or partial response (PR), as assessed per RECIST 1.1 by the investigator.

### **2.7.2 Statistical hypothesis model and method of analysis**

The primary efficacy analysis will be performed on the FAS.

The study targets an ORR of 50%. A response rate of 35% or less is considered as insufficient level of activity for the proposed patient population. Therefore,

$H_0: \text{ORR} \leq 35\%$  will be tested vs  $H_1: \text{ORR} > 50\%$

using a one-sided test with  $\alpha=0.05$  based on Simon's optimal two-stage design ([Simon 1989](#)). If 45 or more responses are seen in 105 total patients (estimated ORR of 42.9%), then  $H_0$  will be rejected and the trial declared positive.

Stage 1 will enroll 43 patients. If the study is terminated early at the end of Stage 1 (16 or fewer responses among 43 patients enrolled to Stage 1), then the study will be considered to have failed to reject  $H_0$ . See [Section 2.11](#) for further details of the stopping criteria for futility. Stage 2 will include an additional 62 patients. The primary analysis will occur when all 105 patients have completed 6 cycles of treatment or discontinued treatment earlier.

The ORR will be estimated and the 90% and 95% Clopper-Pearson (Clopper and Pearson 1934) confidence intervals (CIs) will be provided. The uniformly minimum variance unbiased estimator (UMVUE) and the 90% two-stage CI (Atkinson and Brown 1985) will also be presented. Refer to Section 4.6.4 for additional details.

Clopper-Pearson confidence intervals will be used since the confidence limits based on the normal approximation are not bounded by the  $[0, 1]$  interval, meaning that for rates close to 0 or 1, the upper limit of the normal approximation interval for the proportion could exceed 1 or the lower limit could be negative. The 90% two-stage CI will be presented to correspond to the Simon two-stage p-value.

### 2.7.3 Handling of missing values/censoring/discontinuations

Confirmed PR or CR reported prior to any additional anticancer therapy will be considered as responses in the calculation of the ORR in respect of the number of missed assessments before response.

Patients with a best overall response (BOR) of 'Unknown' or 'Not Assessed per RECIST 1.1' will be considered as non-responders when estimating ORR.

Patients who have disease progression and continue to receive study drug after progression will qualify for PD at the time of progression and will be counted as PD in the derivation of ORR and any other efficacy endpoints.

### 2.7.4 Supportive analyses

Listings of calculated overall lesion response based on raw measurements reported by the investigator (Source 2 in Table 4-3) will be generated. Waterfall plots representing the best percentage change from baseline in the sum of the longest tumor diameters for target lesions will be produced.

## 2.8 Analysis of secondary variables

### 2.8.1 Efficacy

All tumor response related endpoints under the secondary efficacy objectives (DOR, TTR, DCR, PFS) will be analyzed as per investigator assessment and as per the BIRC. Confirmation of response is required for all response endpoints, as per RECIST 1.1.

All secondary endpoint analyses will be performed based on the FAS, unless otherwise specified.

No adjustment for multiple testing will be made.

The key secondary efficacy endpoints are

- ORR by BIRC
- DOR by investigator assessment and by BIRC
- DCR by investigator assessment and by BIRC
- TTR by investigator assessment and by BIRC

Other secondary efficacy endpoints are

- PFS by investigator assessment and by BIRC
- OS

The definitions and details on the derivation of the secondary endpoints are given in the LDK378A2203 protocol. Further details and notes needed for programmatic implementation of RECIST 1.1 guidelines are provided in [Section 4.6.1](#).

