Data analysis	
The cut-off date for the primary analysis of this trial will be the time when all 105 patients have completed 6 cycles of treatment or have discontinued treatment. The ORR per RECIST 1.1 by investigator assessment and by BIRC assessment will be estimated and the 90% confidence interval (CI) provided. If the true ORR is 50% (under the alternative hypothesis), approximately 105 patients are required to reject the null hypothesis of $ORR \leq 35\%$ with a one-sided alpha of 0.05 based on Simon's optimal two-stage design. If 45 or more responses are seen in 105 total patients (estimated ORR of 42.9%), then the null hypothesis will be rejected and the trial declared positive. If the study is terminated early at the end of Stage 1, then the study will be considered to have failed to reject the null hypothesis. The uniformly minimum variance unbiased estimator (UMVUE) and the 90% CI from Atkinson and Brown (1985) will also be presented.
 
DOR will be listed by patient and may be described using Kaplan-Meier methods and relevant statistics if appropriate. DCR and OIRR will be estimated and the 90% CI provided. TTR, PFS, and OS will be described using Kaplan-Meier methods and appropriate summary statistics.
 
Adverse events and laboratory abnormalities will be summarized and listed.

Key words	ALK, NSCLC, LDK378

Amendment 4

Amendment rationale

As of the release date of this amendment the recruitment has been completed and 132 patients have been screened to the study. A total of 124 patients have been treated.

This amendment has been implemented to:

- Update the protocol to include follow up evaluations for hepatic toxicities and work-up guidelines for potential Drug Induced Liver Injury (DILI) cases in order to optimize the patient safety.
- Update the dose guidance modification for QTcF text to provide clarification on monitoring procedure.
- Update the guidance related to corticosteroids use
- Update of the definition of the End of Study
- Editorial changes and text corrections were made for clarification, where required.

Changes to the protocol

Changes to specific sections of the protocol are shown in the track changes version of the protocol using strike through red font for deletions and red underlined font for insertions.

The following sections were changed:

- [List of abbreviations](#) updated with commonly used abbreviations such as R value, TBIL, DILI, EBV, CMV, and HSV

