2.3 Rationale for dose and regimen selection

[REDACTED]

[figure not shown]
3 Objectives and endpoints

[figure not shown]
Objectives and related endpoints are described in [Table 3-1](#) below.

[figure not shown]
[REDACTED]

Table 3-1 Objectives and related endpoints

Objective	Endpoint	Analysis
Primary		
To demonstrate the antitumor activity of LDK378, as measured by overall response rate (ORR) to LDK378 by investigator assessment	ORR per RECIST 1.1 calculated as the proportion of patients with a best overall response defined as complete response or partial response (CR+PR) as assessed by investigator	Refer to Section 10.4.
Key secondary		
To evaluate response related endpoints as assessed by investigator and Blinded Independent Review Committee (BIRC):	The following endpoints will be evaluated by investigator assessment and BIRC per RECIST 1.1:	Refer to Section 10.5.1.
1. Duration of response (DOR)	1. DOR, calculated as the time from the date of the first documented CR or PR to the first documented progression or death due to any cause	
2. Disease control rate (DCR)	2. DCR, calculated as the proportion of patients with best overall response of CR, PR, or SD	
3. Time to Response (TTR)	3. TTR, calculated as the time from first dose of LDK378 to first documented response (CR+PR)	
4. Overall intracranial response rate (OIRR)	4. OIRR calculated as the ORR (CR+PR) of lesions in the brain for patients who have measureable disease in the brain at baseline	
And to assess:	And:	
5. ORR by BIRC assessment	5. ORR (CR+PR) per RECIST 1.1 as assessed by BIRC	
Other secondary		
1. To evaluate the safety profile of LDK378	1. Adverse events and laboratory abnormalities	Refer to Section 10.5.2.
2. To evaluate progression-free survival (PFS)	2. PFS, defined as time from first dose of LDK378 to progression or death due to any cause, as assessed by BIRC and investigator assessment	
3. To evaluate overall survival (OS)	3. OS, defined as time from first dose of LDK378 to death due to any cause	

Objective	Endpoint	Analysis
		

4 Study design

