10.5 Secondary objectives

All secondary efficacy assessments (DOR, TTR, DCR, PFS, and OIRR) will be analyzed as per investigator assessment and as per the BIRC. Confirmation of response is required for all response endpoints, as per RECIST 1.1.

All secondary analyses will be performed based on the FAS, unless otherwise specified.

No adjustment for multiple testing will be made.

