10.5.2 Other secondary efficacy objectives

Progression-free survival

Progression-free survival (PFS) is defined as the time from the date of first dose of LDK378 to the date of first documented disease progression per RECIST 1.1 or death due to any cause.

A patient who has not progressed or died at the date of the analysis or when he/she receives any further anticancer therapy in the absence of disease progression will be censored at the time of the last adequate tumor evaluation before the earlier of the cut-off date or the anticancer therapy date. By default, if disease progression or death is documented after one single missing tumor evaluation, the actual event date of disease progression/death will be used for the PFS event date. If disease progression or death is documented after two or more missing tumor evaluations, the PFS time of these patients will be censored at the date of the last adequate tumor evaluation without PD.

PFS assessed by the investigators and the BIRC will be described using Kaplan-Meier methods and appropriate summary statistics.

Overall survival

Overall survival (OS) is defined as the time from the date of first dose of LDK378 to the date of death due to any cause. OS time for patients who are alive at the end of the study or are lost to follow-up will be censored at the date of last contact.

OS will be described using Kaplan-Meier methods and appropriate summary statistics.

Overall intracranial response rate (OIRR)

OIRR is calculated based on response assessments in the brain for patients having measurable brain metastases at baseline (i.e. at least one target lesion in the brain). OIRR is defined as the ORR based on target and non-target lesions in the brain and defined as the proportion of patients with a best overall confirmed response of CR or PR in the brain, as assessed per RECIST 1.1 by the investigator and by BIRC.

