#### 1.2.2 Secondary objectives

The key secondary objectives are to evaluate response related endpoints as assessed by both investigator and Blinded Independent Review Committee (BIRC), unless otherwise specified, as per RECIST 1.1:

- duration of response (DOR)
- disease control rate (DCR)
- time to response (TTR)

and to assess

- ORR by BIRC assessment.

Other secondary objectives are to evaluate:

- the safety profile of LDK378
- progression-free survival (PFS) as assessed by both investigator and BIRC
- Overall survival (OS).

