## Duration of response

Among patients with a confirmed response (PR or CR), DOR is defined as the time from first documented response (PR or CR) to the date of first documented PD or death due to underlying cancer. If a patient has not had an event, DOR is censored at the date of last adequate tumor assessment.

The censoring and event date options to be considered for the main analysis are presented in [Table 2-1](#).

Table 2-1 Outcome and event dates for DOR and PFS analyses

	Situation	Date	Outcome
A	No baseline assessment	Date of first dose of study drug*	Censored
B	Progression at or before next scheduled Assessment	Date of progression	Progressed
C1	Progression or death after exactly one missing assessment	Date of progression (or death)	Progressed
C2	Progression or death after two or more missing assessments	Date of last adequate assessment†	Censored
D	No progression	Date of last adequate assessment •	Censored
E	Treatment discontinuation due to 'Disease progression' without documented progression, i.e. clinical progression based on investigator claim	N/A	Information ignored. Outcome derived based on radiology data only.
F	New anticancer therapy given	Date of last adequate assessment •	Censored
G	Deaths due to reason other than deterioration of 'Study indication'	Date of last adequate assessment •	Censored (only applicable to DOR)

• The rare exception to this is if the patient dies no later than the time of the second scheduled assessment as defined in the protocol in which case this is a PFS event at the date of death

• After the last adequate tumor assessment. "Date of next scheduled assessment" is defined in Section 3.2.7 of Section 14 (Appendix II) of the LDK378A2203 protocol

DOR will be described in tabular and graphical format using Kaplan-Meier methods including estimated median (in months) with 95% CI, 25th and 75th percentiles (Brookmeyer and Crowley 1982, Klein and Moeschberger 2005) and Kaplan-Meier estimated probabilities with confidence intervals (Kalbfleisch and Prentice 2002) at several time points (including at least 4, 8, 12, 15, 18 months).

These analyses will be performed separately based on investigator assessment and based on BIRC assessment.

Refer to Section 4.6.3 for further details regarding derivation of Kaplan - Meier estimates.

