**Table 4-3 Sources for overall lesion response**

Source 1	Investigator (local radiology) reported overall lesion response
Source 2	Calculated overall lesion response based on raw (i.e. individual lesion) measurements from Investigator (local radiology)
Source 3	BIRC (Blinded Independent review committee) reported overall lesion response

In this study, Source 1 will be used for the primary endpoint derivation and other secondary endpoint calculations based on investigator assessment (ORR, DCR, DOR, TTR and PFS) and Source 2 will be listed against Source 1 and discrepancies between calculated and reported responses assigned by investigator will be identified. Source 3 will be used to calculate ORR, DCR, DOR, TTR and PFS by BIRC.

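### The final-analysis SAP omits intracranial response without declaring it, and its duration of response counts a narrower death event than the protocol's

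*SAP*

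**What the plan says.** **Protocol.** Table 3-1 names five key secondary endpoints: DOR, DCR, TTR, OIRR and ORR by BIRC. OIRR is the fourth: "OIRR calculated as the ORR (CR+PR) of lesions in the brain for patients who have measureable disease in the brain at baseline". Section 10.5 requires the analysis: "All secondary efficacy assessments (DOR, TTR, DCR, PFS, and OIRR) will be analyzed as per investigator assessment and as per the BIRC". Section 10.5.2 gives the population, "OIRR is calculated based on response assessments in the brain for patients having measurable brain metastases at baseline", and asks for confirmed CR or PR in the brain by both assessors. The protocol summary adds: "DCR and OIRR will be estimated and the 90% CI provided". For DOR, Table 3-1 and 10.5.1 count death whatever its cause.

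**SAP (version 1.0, final analysis).** Section 1.2.2 lists DOR, DCR, TTR and ORR by BIRC as key secondary objectives. Section 2.8.1 repeats the protocol sentence without OIRR: "All tumor response related endpoints under the secondary efficacy objectives (DOR, TTR, DCR, PFS) will be analyzed as per investigator assessment". Its lists of key and other secondary endpoints do not contain OIRR either. Section 4.6.2 assigns response sources by endpoint, again without it: "Source 3 will be used to calculate ORR, DCR, DOR, TTR and PFS by BIRC". DOR runs from first response "to the date of first documented PD or death due to underlying cancer". Row G of Table 2-1 puts this into effect by censoring deaths from other causes at the last adequate assessment, for DOR only.

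**The concern.** The SAP is the document the programmers follow. Followed as written, it produces no OIRR result for the final report, and the reader is not told that the endpoint was dropped.

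For DOR, it yields an estimate on an event the protocol no longer uses. The protocol's Amendment 2 rationale says that the any-cause definition was adopted after health authority feedback, because attributing death to the cancer is difficult in this disease. Row G brings that attribution back. It also makes the SAP inconsistent with itself: PFS counts any death, so the same death in a responder without progression could be a PFS event and a censored DOR.

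**Working it through.** **1. The current texts side by side**

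| Item | Protocol | SAP |
|---|---|---|
| OIRR status | Key secondary (summary, Table 3-1); placed under other secondary in 10.5.2 | Absent from 1.2.2 and from both lists in 2.8.1 |
| OIRR assessors | Investigator and BIRC (10.5, 10.5.2) | No source assigned in 4.6.2 |
| OIRR estimate | Rate with 90% CI (summary) | None planned |
| Death as DOR event | Any cause (Table 3-1, 10.5.1) | Underlying cancer only (2.8.1); other deaths censored (Table 2-1, row G) |
| Declared in SAP Table 3-1 | n/a | No. The four declared changes are the Safety Set, the Per-Protocol Set, the laboratory frequency tables and the CI level |

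SAP 2.8.1 also says that the secondary endpoint definitions are those in the protocol, so its DOR text conflicts with its own pointer.

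**2. Where the wording comes from.** The amendment log shows that Amendment 2 both added OIRR and changed the DOR event. Other SAP text also predates the current protocol. Section 1.1 still requires prior chemotherapy including a platinum doublet, while Protocol 5.2 admits chemotherapy-naïve patients. SAP Table 3-1 attributes a follow-up scan after more than 8 weeks to the protocol's Per-Protocol Set, while Protocol 10.1.3 says more than 7. This points to carried-over text rather than a decision.

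**3. Plan's own figures.** The plan gives no number for OIRR or DOR. Its design figures concern ORR only and reproduce exactly: success probability 0.0487 at a true ORR of 35% (stated 0.049) and 0.9000 at 50% (stated 0.900). Nothing here changes them.

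**4. Size for DOR (illustrative).** Suppose event times are exponential with total hazard λ, and a share s of DOR events are non-cancer deaths. Censoring those deaths leaves the hazard λ(1 − s), so the reported median is the any-cause median divided by (1 − s). The starting value of 8.2 months is the phase I median in Protocol 1.2.1.2.2, treated here as an any-cause median. The values of s are assumed.

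| s | Median under SAP rule | Increase |
|---|---|---|
| 5% | 8.2/0.95 = 8.6 months | 5.3% |
| 10% | 8.2/0.90 = 9.1 months | 11.1% |
| 15% | 8.2/0.85 = 9.6 months | 17.6% |

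The 12-month rate would move from 36.3% to 38.2%, 40.1% and 42.2%.

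A rough guide to s: Protocol 1.2.1.2.1 lists 4 + 8 × 1 = 12 fatal adverse reactions in 255 patients, or 4.7%. With 124 treated patients and response rates of 50% (target) to 62% (crizotinib-naïve at 750 mg, Protocol Table 1-2), there would be 62 to 77 responders. Then 62 × 12/255 = 2.9 and 76.9 × 12/255 = 3.6, so about 3 to 4 deaths. If every responder had a DOR event, s would be about 4.7%. If 70% did, s would be 4.7/0.70 = 6.7%. The lower rows are therefore the more plausible.

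**5. OIRR.** The documents do not say how many patients have a brain target lesion. If the number were 10, 20 or 30 and half responded (assumed), the exact 95% CI would be 18.7–81.3%, 27.2–72.8% or 31.3–68.7%. These intervals show only the precision an OIRR table might have. The loss is the missing result itself.

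**6. Laboratory tables (minor).** Protocol Table 7-3 collects lipase. The SAP keeps it in the pancreatitis events of special interest and in the graded laboratory listings, but leaves it out of the biochemistry shift tables that include amylase.

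**The case against.** The DOR conflict is plain in the text. The stronger objections concern OIRR and the size of the effect.

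- **Another document may cover OIRR.** This SAP is for the final analysis, and it refers to an earlier analysis plan that is not among these documents. OIRR may have been planned there. But the protocol (4.3 and 10) says all available data will be analysed at the final cut-off. When this SAP drops the Per-Protocol Set analyses it says so, whereas it is silent on OIRR.
- **Redaction.** Some SAP headings after 1.2.2 and within 2.8 are blacked out, so a mention of OIRR there cannot be excluded. The lists where it belongs and the table of changes are legible, and it is not in them.
- **General pointers to the protocol (SAP 2.1, 2.8.1).** A general reference does not override an explicit censoring row or restore an endpoint to closed lists.
- **Classification.** Protocol 10.5.2 files OIRR under other secondary objectives. It is secondary either way and missing from both SAP lists.
- **Weak proxies for size.** This stands. The 12 deaths are in all patients, not responders, and need not precede progression. Some may be cancer-related, and other non-cancer deaths may be missed. The 8.2 months come from a mixed population (79 of 114 had prior crizotinib), and the protocol does not say which death rule was used. The 15% row would need only about 31% of responders to have an event (4.7/15), or about three times the guide rate.
- **Appendix II.** Protocol 10.5.1 sends the reader there for DOR censoring rules, and its body is not legible. Row G may come from it, so it needs checking.

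**Conclusion.** The concern holds on the text. The current SAP omits OIRR from every legible list where it belongs and computes DOR on a different event from the current protocol. It declares neither change.

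The direction for DOR is certain: censoring non-cancer deaths lengthens the estimate or leaves it unchanged. The size cannot be taken from the documents. An increase in the median of 5% to 18% rests on exponential times and an assumed 5% to 15% share of non-cancer deaths, and the rough guide favours the lower end.

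The primary ORR test, its alpha and its power are untouched, and ORR by BIRC, DCR, TTR, PFS and OS remain planned. Both affected endpoints are descriptive. This should be corrected, but it does not threaten the trial's main conclusion.

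**What to change.** 1. **OIRR.** Add it, by investigator and by BIRC, to SAP 1.2.2, 2.8.1 and 4.6.2. Use confirmed CR or PR in the brain, with FAS patients who have at least one brain target lesion at baseline as the denominator. Give an exact 95% CI, the level SAP Table 3-1 sets for secondary endpoints. Name a brain-only response derivation for each assessor, because Sources 1 and 3 are whole-patient responses. If the removal was intended, declare and justify it in SAP Table 3-1.
2. **DOR.** Define the event as progression or death from any cause and delete row G of Table 2-1. Check the DOR censoring rules in Protocol Appendix II and reconcile them if they contain a matching row.
3. **Lipase.** Add lipase (increased) to the biochemistry shift tables.
4. **Editorial.** Bring the population description in SAP 1.1 into line with current Protocol 5.2. This changes no analysis, because the FAS is all treated patients.

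The cost is SAP text, a brain-specific derivation and one OIRR table per assessor, one changed DOR derivation and one shift table. The protocol already schedules brain imaging for patients positive at baseline and already collects deaths and lipase, so no new data collection is needed.
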